5.1.1. Overview of TEAEs

An overview of TEAEs reported through the study will be provided for each NHL subtype. The overview will include summaries of subjects with TEAEs, TEAEs related to study treatment, TEAEs of maximum toxicity grade of 1 to 5, SAEs, TEAEs leading to discontinuation of study treatment and summary of TEAEs result in death.

5.1.2. All TEAEs

- Incidence of TEAEs by MedDRA SOC and preferred term
- List of subjects with any TEAEs

5.1.3. Toxicity Grade 3 or 4 TEAEs

- Incidence of toxicity grade 3 or 4 TEAEs, by MedDRA SOC and preferred term

5.1.4. Treatment-emergent Infusion related reactions

- Incidence of treatment-emergent infusion related reactions, by MedDRA SOC and preferred term
- Toxicity grade of treatment-emergent infusion related reactions
- List of infusion related reactions

5.1.5. Study Treatment-Related TEAEs

- Incidence of TEAEs considered by the investigator to be related to study treatment, by MedDRA SOC, and preferred term
- Incidence of TEAEs with toxicity grade 3 or 4 considered by the investigator to be related to study treatment, by MedDRA SOC and preferred term

5.1.6. Serious Adverse Events (SAEs)

- Incidence of treatment-emergent SAEs, by MedDRA SOC and preferred term
- Incidence of treatment-emergent SAEs considered by the investigator to be related to study treatment, by MedDRA SOC, and preferred term

5.1.7. TEAEs Leading to Discontinuation of Study Treatment

A summary of number of subjects who discontinued study treatment because of 1 or more TEAEs by MedDRA system-organ class and preferred term will be provided. This table includes AEs leading to discontinuation of study treatment for those subjects indicated as having discontinued study treatment due to an adverse event on the end of treatment CRF page.

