##### **Determination of CD38 and CD59 Expression:**

During screening, subjects will be required to provide tumor samples for assessment of CD38 expression based on central testing using investigational IHC methodology under development (Section [9.1.2](#)). An additional fresh biopsy should be obtained whenever possible even if an archival sample is provided. Fresh tumor samples can be either lymph node excision or core needle biopsy; fine needle aspirates are not acceptable.

In addition to evaluating CD38 expression, fresh or archived biopsy samples may be evaluated in all subjects to identify markers predictive of response to daratumumab or prognostic markers for disease progression. Paraffin-embedded, formalin-fixed tumor tissue may also be subjected to DNA (eg, somatic mutations) and RNA analysis (eg, GEP, qRT-PCR, or RNA-seq) to determine if specific mutations or transcriptomic profiles (translocations, deletions, inversions, genes involved in B-cell signaling pathways, CD38 signaling pathways, or others) are associated with daratumumab response. Comparison of CD38 IHC results may be made to transcriptomic data. In addition to CD38, CD59 expression will be measured by IHC in a designated laboratory as an exploratory biomarker. CD59 is a complement inhibitory protein and can contribute to resistance to CDC, which may be important for daratumumab response.

A subject's study treatment should be discontinued if:

- The investigator believes that for safety reasons (eg, adverse event) it is in the best interest of the subject to discontinue study treatment
- The subject becomes pregnant
- The subject withdraws consent for administration of study treatment
- The subject initiates treatment with a prohibited medication
- The subject received concurrent (non-protocol) treatment for NHL
- The subject experiences unacceptable toxicity, including IRRs described in Section 6.3.3
- The subject's dose of daratumumab is held for more than 4 weeks (Cycle 1 to Cycle 6) or 6 weeks (Cycle 7 and beyond) should have study treatment discontinued, unless, after consultation with the sponsor and review of safety and efficacy, continuation is agreed upon
- The subject experiences disease progression (please see below). Relapse from CR is not considered as disease progression

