A subject who experiences a second primary malignancy that cannot be treated by surgery alone must be withdrawn from the study. However, a subject who develops a malignancy that can be cured surgically may continue to receive the assigned study treatment and should continue to be followed for subsequent progression of lymphoma.

The primary reason for discontinuation of study treatment is to be recorded in the eCRF.

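### SAP 5.1.7 ties the table of TEAEs leading to discontinuation to a single recorded primary reason, so the count can be too low

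*SAP*

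**What the plan says.** SAP 5.1.7 gives the purpose of the table as "A summary of number of subjects who discontinued study treatment because of 1 or more TEAEs", broken down by system organ class and preferred term. Its next sentence says the table holds the AEs leading to discontinuation "for those subjects indicated as having discontinued study treatment due to an adverse event on the end of treatment CRF page".

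The protocol's section on stopping study treatment (10.2, the list that ends just before 10.3) says: "The primary reason for discontinuation of study treatment is to be recorded in the eCRF". The same list gives several separate grounds for stopping. Among them are:

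- the safety ground: "The investigator believes that for safety reasons (eg, adverse event) it is in the best interest of the subject to discontinue study treatment"
- toxicity: "The subject experiences unacceptable toxicity, including IRRs described in Section 6.3.3"
- a long interruption: "dose of daratumumab is held for more than 4 weeks" in Cycles 1 to 6, with a longer limit from Cycle 7
- consent: "The subject withdraws consent for administration of study treatment"

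SAP 5.1.1 repeats the discontinuation item as a line of the overview table and gives no derivation of its own. SAP 3.2 summarises and lists the reasons for stopping that investigators gave. SAP 1.3 names AEs leading to treatment discontinuation among the safety outputs for the interim analysis.

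**The concern.** The stated purpose and the rule for entry do not match. The purpose concerns cause: did a TEAE lead to stopping? The rule adds a second condition, that adverse event was the reason entered on the end-of-treatment page. With one primary reason per subject, an AE that contributed to stopping can lose its place to another entry. A subject who withdraws consent for treatment after an infusion reaction is one example. A subject whose dose was held too long because of an AE is another.

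Two things are at stake. The tolerability figure can only err in the favourable direction, and it depends partly on how each site ranks competing reasons. The rule may also outlast the interim: SAP section 1 says this document becomes the study SAP if the futility criteria are met.

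**Working it through.** The plan gives no figure for this point, so there is none to reproduce. The check compares the texts and then sizes one subject.

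**Step 1: the two conditions.** Let A be the treated subjects with at least one TEAE attributed to discontinuation, and E the treated subjects whose end-of-treatment reason is adverse event.

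| Quantity | Source | Count |
|---|---|---|
| Stated purpose | SAP 5.1.7, first sentence | A |
| Rule for entry | SAP 5.1.7, second sentence | A and E |
| Disposition count for adverse event | SAP 3.2 | E |

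The second sentence of 5.1.7 speaks of AEs that led to discontinuation, so the SAP itself presupposes that A can be identified.

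**Step 2: direction.** Subjects in both A and E are a subset of A. The shortfall is the number in A but not in E. It is zero or positive, never negative.

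**Step 3: can a subject be in A but not in E?** Protocol 10.2 records one primary reason and lists the prolonged hold and withdrawal of consent apart from the safety ground. A TEAE can lie behind either. If the CRF offers these as separate reasons, such a subject can correctly carry a primary reason other than adverse event.

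**Step 4: is the subject recovered elsewhere in the count?** The overview line in 5.1.1 has no derivation of its own. The disposition summary in 3.2 uses the investigator's stated reason. Neither document describes a comparison of the AE record with the end-of-treatment page. By contrast, 5.1.8 selects TEAEs by the action they led to, with no end-of-treatment condition, and 5.1.9 works from the AE page.

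**Step 5: size per subject.** The Stage 1 targets in SAP 1.1 are 20 for MCL and 15 each for DLBCL and FL, 50 in total (SAP 1.2). If k subjects are left out of n treated, the reported proportion falls by k/n. The values of k are assumptions, since the documents give no basis for estimating it.

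| k (assumed) | MCL, n = 20 | DLBCL or FL, n = 15 | All, n = 50 |
|---|---|---|---|
| 0 | 0 | 0 | 0 |
| 1 | 1/20 = 5.0 points | 1/15 = 6.7 points | 1/50 = 2.0 points |
| 2 | 2/20 = 10.0 points | 2/15 = 13.3 points | 2/50 = 4.0 points |

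For example, if 3 of 15 subjects had a TEAE attributed to stopping and one carried another primary reason, the table would show 2/15 = 13.3% instead of 3/15 = 20.0%.

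**The case against.** The strongest reply is that the mechanism turns on a form that is not in the documents. The list in Protocol 10.2 gives grounds for stopping, not CRF codes. Unacceptable toxicity, including infusion reactions, may well be coded as adverse event, and so may a hold caused by an AE. If so, few or no subjects are lost. This stands: a reader might infer that toxicity-driven stops will be missed, but the documents show only that they can be.

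The SAP also says the table includes these events, not that it excludes all others. That is literally true, but no other route into the table is described. If a wider rule is meant, it should be stated.

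A reader might also infer that safety events are hidden. The documents do not support that. Delays and dose modifications are reported in SAP 3.3 and 5.1.8, infusion reactions in 5.1.4, fatal AEs in 5.1.9, deaths in 5.2, and all TEAEs in 5.1.2. SAP 3.2 lists each subject who stopped, with the reason. With 15 to 20 subjects per cohort, these can be read against each other. What can be lost is the attribution to discontinuation in one table and its overview line.

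Nor do the documents support the reading that this could change the Stage 2 decision by rule. The futility guideline in SAP 1.1 rests on ORR, and no threshold uses the discontinuation count. It is one item in the totality of Stage 1 data.

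Finally, the primary-reason rule keeps this table in step with disposition, and selecting on AE attribution can bring in subjects whose main reason was progression. This is a fair description of the trade-off. It does not rescue the present text, whose first sentence asks about cause and not about the primary reason.

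**Conclusion.** The point holds as a weakness in the definition of one descriptive safety table. The rule for entry in SAP 5.1.7 is narrower than the table's stated purpose, and the difference can only lower the count. Each subject affected at Stage 1 is worth 5.0 points in MCL or 6.7 points in DLBCL or FL.

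The number affected is unknown and may be zero. The conclusion assumes that the second sentence of 5.1.7 is the operative rule, that the CRF allows one primary reason, and that at least some reasons other than adverse event can apply when a TEAE contributed to stopping. ORR, the futility rule and power are untouched. It ranks as a cheap improvement.

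**What to change.** In SAP 5.1.7, and in the matching line of 5.1.1, include every treated subject who has either:

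- at least one TEAE recorded as leading to discontinuation of daratumumab, at the level of the individual AE, where the CRF collects this; or
- adverse event as the end-of-treatment reason.

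Keep the primary-reason count in the disposition table (SAP 3.2). Add a listing of subjects for whom the two sources differ, and name the data source in the SAP. Do not add a criterion for an AE that caused the hold which ended treatment unless the CRF records that link; neither document shows that it does. SAP 5.1.8 does not name its data source, so it cannot be taken as proof that an AE-level action field exists. The CRF should be checked first.

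The cost is a few lines of SAP text, one programming rule and one listing. No rule on treatment or stopping changes. The reported rate may be slightly less favourable and may differ from the disposition table, because it can include subjects whose primary reason was something else. A footnote should say so.

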5.1.8. TEAEs Leading to Cycle Delays or Dose Modifications

Incidence of TEAEs leading to treatment cycle delays or dose modifications will be summarized by MedDRA SOC and preferred term. This table will include TEAEs leading to cycle delays or at least 1 of study treatments dose modifications, the dose modifications include dose delays or dose skipping.

5.1.9. AEs with Outcome Death

Incidence of AEs with outcome of “FATAL” or toxicity grade of 5 from AE page will be summarized by MedDRA SOC and preferred term.

5.2. Deaths

5.2.1. All Deaths

A summary of death within 30 days of last study treatment and cause of death will be tabulated overall and by NHL subtype. Specifically, the number of subjects who died during the study will be summarized for all treated population. The primary cause of death collected on CRF page will be reported. If the primary cause of death reported is an AE, the number of subjects who have a treatment related AE and unrelated AE will be further reported. Similar summaries will be presented for all death.

A listing of death information will be provided.

5.3. Clinical Laboratory Tests

The evaluation of clinical laboratory tests will focus on the following selected laboratory analytes:

Hematology panel:

- hemoglobin
- platelet count
- white blood cell (WBC) count with absolute neutrophils and lymphocytes

Blood chemistry panel:

- | | |
|-----------------------------------|------------------------|
| -sodium | -alkaline phosphatase |
| -potassium | -lactate dehydrogenase |
| -creatinine | -uric acid |
| -total bilirubin | -calcium |
| -direct bilirubin | -total Protein |
| -aspartate aminotransferase (AST) | -albumin |
| -alanine aminotransferase (ALT) | -Creatinine clearance |

Blood samples for serum hematology are taken at the screening visit, on Days 1, 8, 15 and 22 of Cycles 1-2, Days 1 and 15 of Cycles 3-6, Day 1 of Cycles 7+ and at the End-of-Treatment visit. Results of hematology tests must be evaluated before study drug administration. Blood samples for biochemistry are taken at the screening visit, on Day 1 of each treatment cycle and at the End-of-Treatment visit.

Descriptive statistics (mean, standard deviation, median, range) will be used to summarize observed laboratory values and change from baseline in observed value at each scheduled visit for each NHL subtype.

The worst toxicity grade in hematology and chemistry during the treatment will be summarized by NHL subtype and toxicity grade.

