2.7. Baseline Measurement

Baseline measurement is defined as the closest non-missing measurement taken on or prior to the date of first study agent administration (including time if available). If the first study treatment date is missing, the corresponding visit date should be used.

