5. SAFETY

Safety assessment will be evaluated through AEs, clinical hematology and chemistry laboratory tests, ECGs, vital signs measurements, physical examination findings, and assessment of ECOG performance status score. All toxicities will be graded according to the NCI CTCAE Version 4.03. Safety analyses will be based on all treated population and presented by each NHL subtype.

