5.1. Adverse Events

All adverse events whether serious or non-serious, will be reported from the time a signed and dated ICF is obtained until 30 days after the last dose of study treatment, until the subject withdraws consent for study participation, or until the subject starts subsequent anticancer therapy, whichever occurs first. AEs will be recorded in standard medical terminology and graded according to the National Cancer Institute Common Terminology Criteria for Adverse Events (NCI-CTCAE), Version 4.03. For AE reporting, the verbatim term used in the CRF by investigators to identify adverse events will be coded using the latest version of Medical Dictionary for Regulatory Activities (MedDRA) coding dictionary.

Unless otherwise specified, at each level (e.g., system organ class and/or preferred term) of subject summarization in reporting the incidence of the AE, a subject is counted once if one or more events were recorded.

All summaries of AEs will be based on treatment-emergent adverse events (TEAEs). TEAEs are defined as any AE that occurs after start of the first study treatment through 30 days after the last study treatment; or the day prior to start of subsequent anticancer therapy, whichever is earlier; or any AE that is considered drug-related (very likely, probably, or possibly related) regardless of the start date of the event.

The incidence of TEAEs will be summarized overall, by MedDRA system organ class (SOC) and preferred term, by toxicity grade, and by relationship to study treatment administration. Specifically, the following AE summaries will be presented by NHL subtype:

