5.5. Electrocardiogram (ECG)

Electrocardiograms (ECG) will be performed at Screening, Day 1 of Cycle 3 and Cycle 6, and End-of-Treatment visit. If blood sampling or vital sign measurement is scheduled for the same time point as ECG recording, then the procedures should be performed in the following order: ECG(s), vital signs, blood draw.

The number and percentage of subjects with normal, clinically significant or clinically non-significant abnormal 12-lead ECG results will be summarized at each scheduled visit by NHL subtype.

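### SAP 5.3 reports laboratory toxicity only as the worst grade during treatment, so the table cannot separate abnormalities present at entry from new or worsened ones

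*SAP*

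**What the plan says.** SAP Section 5.3 plans two laboratory outputs for each NHL subtype.

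- **Values.** Mean, standard deviation, median and range are used to "summarize observed laboratory values and change from baseline in observed value at each scheduled visit for each NHL subtype".
- **Grades.** "The worst toxicity grade in hematology and chemistry during the treatment will be summarized by NHL subtype and toxicity grade". Grading follows Section 5: "All toxicities will be graded according to the NCI CTCAE Version 4.03".

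The grade output has no baseline column, no condition that the grade must have worsened, and no definition of the treatment period.

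Three other provisions bear on this.

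- Section 2.7 defines baseline: "Baseline measurement is defined as the closest non-missing measurement taken on or prior to the date of first study agent administration".
- Section 5.3 has hematology drawn at screening, "on Days 1, 8, 15 and 22 of Cycles 1-2, Days 1 and 15 of Cycles 3-6, Day 1 of Cycles 7" and later, and at the End-of-Treatment visit. It adds: "Results of hematology tests must be evaluated before study drug administration".
- Section 5.1 has an emergence rule, but for adverse events: "TEAEs are defined as any AE that occurs after start of the first study treatment through 30 days after the last study treatment". There is no counterpart for laboratory grades.

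**The concern.** Subjects in this study have been treated before and may have marrow disease. SAP Section 3.1 summarises baseline marrow infiltration and Section 3.5 the number of prior lines of therapy. Some abnormal blood counts at entry are therefore plausible.

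Section 1.4 states that there is no randomization, and there is no control arm to show how often such abnormalities occur without the drug. The within-subject comparison with baseline has to do that work, and the grade table leaves it out.

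What is at stake is how the descriptive laboratory safety results are read. Section 1.3 includes hematology and chemistry parameters in the interim safety evaluation. Under Section 1, this interim SAP becomes the study SAP if futility is met, so these tables could be the final ones.

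**Working it through.** The plan states no figure on this point, so there is nothing to reproduce. The check is a reading of the sections against each other, followed by an illustration.

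**1. Can the grade table separate old from new?** Take three hypothetical subjects and one analyte.

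| Subject | Baseline grade | Worst grade after first dose | Row in planned table | Cell in a shift table |
|---|---|---|---|---|
| A | 3 | 3 | Grade 3 | 3 to 3 (no change) |
| B | 0 | 3 | Grade 3 | 0 to 3 (new) |
| C | 3 | 4 | Grade 4 | 3 to 4 (worsened) |

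A and B fall in the same row of the planned table. C cannot be told apart from a subject who went from grade 0 to grade 4.

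**2. Do the value summaries fill the gap?** Only in part. They show the average change at a visit. The range shows the extremes at screening and the largest individual change. They are computed on the measured value, one visit at a time, so they do not link a subject's starting grade to that subject's worst grade.

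**3. Is the pre-dose sample excluded?** The text does not say.

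- Scheduled hematology samples through Cycle 6: 4 in each of Cycles 1-2 and 2 in each of Cycles 3-6, so 4 x 2 + 2 x 4 = 16, including Cycle 1 Day 1.
- Results must be evaluated before dosing, so the Cycle 1 Day 1 value can be a pre-dose value. Under Section 2.7 it can be the baseline itself.
- Section 2.1 summarises data collected by cycle, laboratory data among them, under the nominal cycle, so this sample carries the label Cycle 1.

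If it is counted as during treatment, a subject at grade 3 before the first dose who then improves to grade 1 is still tabulated at grade 3. If it is excluded, the same subject is tabulated at grade 1.

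**4. Does another rule cover it?** The treatment-emergent definition in Section 5.1 applies to adverse events. Section 5.4 (vital signs) and Section 5.6.1 (ECOG) use change from baseline. No shift table or worsening rule for laboratory grades appears in the SAP or in the protocol text available for this review.

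**5. Illustration of size.** Let p be the share of subjects who enter at grade 3 or worse for a given analyte and stay there, and n the Stage 1 size from Section 1.2. The documents do not give p; 5% to 15% is an assumption. The number counted at grade 3 or worse with no change is n x p.

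- MCL, n = 20: 20 x 0.05 = 1 to 20 x 0.15 = 3.
- DLBCL or FL, n = 15 each: 15 x 0.05 = 0.75 to 15 x 0.15 = 2.25.

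One subject is 1/20 = 5 percentage points in MCL and 1/15 = 6.7 points in DLBCL or FL. For such subjects, a table restricted to new or worsened grades would show 0.

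**The case against.** **The prevalence is not known.** This stands. Marrow infiltration and prior therapy make abnormal counts plausible; they do not establish grade 3 or worse. One range cannot fit analytes as different as lymphocytes and sodium, and the illustration also assumes persistence. Most of the protocol's eligibility and statistical sections were not in the text available for this review. Entry limits on laboratory values could lower p, and a baseline comparison could already be specified there.

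**A reader might infer that the plan overstates drug toxicity.** The documents do not support that. Toxicity grade in Section 5.3 is a CTCAE severity label, and the table attributes nothing to daratumumab. Emergence and relatedness are handled in Sections 5.1 to 5.1.5, including grade 3 or 4 events related to treatment. What stands is narrower: the laboratory table cannot by itself separate pre-existing grades from new ones.

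**A reader might infer that baseline is ignored in the laboratory section.** It is not, since change from baseline in values is summarised. Only the grade output omits it.

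**A reader might extend the point to ECGs.** Section 5.5 plans normal and abnormal categories in which "12-lead ECG results will be summarized at each scheduled visit by NHL subtype", and Screening is one of those visits. The baseline distribution is therefore shown beside the later ones. A within-subject cross-tabulation is absent, but an entry abnormality is not merged into an on-treatment result, so the flaw is not the same.

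**No decision rests on this table.** Correct. The futility guideline in Section 1.1 uses response counts, and no threshold is set on laboratory grades.

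**Conclusion.** The point holds for the SAP as written and is minor. The only graded laboratory output does not distinguish an abnormality carried in from one that arose or worsened on treatment, and the period it covers is undefined at its start. With no control arm, the reader cannot recover the distinction from elsewhere in the planned laboratory summaries.

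The size cannot be stated from the documents. The figure of 1-3 of 20 MCL subjects depends entirely on the assumed 5-15% and on persistence of the abnormality. The consequence is confined to descriptive laboratory safety. The conclusion is conditional on the protocol's safety-analysis section not already requiring a shift by grade.

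**What to change.** In SAP Section 5.3:

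1. Replace the worst-grade table by a cross-tabulation, for each gradeable analyte and NHL subtype, of baseline grade (Section 2.7) against worst grade after the first dose, with a row for missing baseline. The planned worst-grade counts remain visible as the column totals.
2. From it, report the number with a grade 3 or 4 value among subjects at grade 2 or lower at baseline, and the number reaching grade 4 among those at grade 3 at baseline, each with its denominator.
3. Define the treatment period for laboratory grades as starting after the first dose and ending at a stated point, and say that the pre-dose Cycle 1 Day 1 sample is excluded.

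An ECG shift table from Screening is optional.

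The cost is programming only. The screening and Day 1 values are already collected, and the baseline definition and grading scale are already in the SAP.
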